We will use grounded theory methods to analyze interview data. These methods lay out a systematic set of inductive procedures for developing categories of information, organizing data in terms of these categories through coding, connecting the categories, and deriving from these connections an empirically grounded theory[73].

Analysis, Aim 4

Aim 4.1. We will measure prevalence of STIs in up to 150 HIV-negative women who want to conceive a child while at risk for HIV exposure.

Aim 4.2. We will measure six-month incidence of STIs in up to 150 HIV-negative women who conceive or want to conceive a child while at risk for HIV exposure.

Hypothesis 4.2. We expect a higher incidence of condomless sex leading to a higher STI incidence among women who choose PrEP as part of a safer conception strategy compared to women who do not take PrEP.

We intend to evaluate up to 150 HIV-negative women entering the study and estimate the prevalence of any STI and each of the specific STIs. Based on prior work, we anticipate the incidence of any STI will be approximately 35%[74] and that 2 out of 3 women[75] will want to start PrEP. We would have 82% power for a difference of 43% (PrEP group) vs 20% (no PrEP group) using a Chi-square test ($\alpha=0.05$, two-sided).

For Aim 4.1, we will use logistic regression first to test covariates as predictors of having a STI at baseline and then to develop an initial model predicting STI. This model will be applied to the STI incidence data through six months to assess operating characteristics. For Aim 4.2, we will use a logistic regression model predicting incident STIs over six months including PrEP in all models and then adding the number of condomless sex acts to the model. If the number of

condomless sex acts is a significant predictor and there is a substantial reduction in the odds ratio (OR) for PrEP when the number of condomless sex acts is included in the model, then we will conclude that this is a mediator of the PrEP effect.

XV. MONITORING AND QUALITY ASSURANCE

The Ugandan PI will be responsible for continuous data and safety monitoring of all study participants and for alerting the US PI if unexpected concerns arise. Serious adverse events (e.g. physical or emotional injury) will be reported to all involved IRBs according to the guidelines of each IRB (i.e., within ten days for the Partners' IRB) and to Gilead who will be providing study drug.

Any protocol violations will be reported within the required timeframe (as per MUST IRB / Partners IRB requirements).

All study-related information will be stored securely at the study site. All participant information will be stored in areas with limited access. Data collection will be labelled only by a participant identification number to maintain participant confidentiality. All records that contain names or other personal identifiers, such as locator forms and informed consent forms, will be stored separately from study records labelled with the participant identification number. All databases will be secured with password-protected access systems. The master list linking participant name to study identification number and other identifying information in study files will be retained for six years after the study is completed; after that time, the link will be destroyed.

We will review the data bi-annually with particular attention to possible adverse events (including HIV acquisition, medication-related adverse events, adverse pregnancy outcomes, and social harms) among women participating in this study with a focus on:

- Rate of HIV seroconversion, compared against the anticipated rate of incident HIV infection in the study population.
- Serious adverse events and medication side effects.
- Social harm, including emotional distress (e.g., stigma, compromise of reproductive autonomy).
- Study execution, including enrolment rates, retention, PrEP initiation, and adherence.

XVI. Budget for MUST

	Year 1	Year 2	Year 3
	7/1/16-6/30/17	7/1/17-6/30/18	7/1/18-6/30/19
Personnel	\$74,766	\$74,766	\$74,766
Consultants	\$0	\$0	\$0
STI laboratory fees	\$0	\$2,000	\$12,714
Equipment	n/a	n/a	n/a
Supplies	\$850	\$150	\$0
STI testing supplies	\$0	\$100	\$430
STI shipping fees for confirmatory testing	\$0	\$200	\$800

STI treatment medications	\$0	\$50	\$295
Travel	\$2,846	\$4,346	\$5,862
Subject Costs	\$7,500	\$7,500	\$0
Other	\$64,038	\$63,238	\$69,372
Direct Costs	\$150,000	\$150,000	\$150,000
Indirect Costs	\$15,000	\$15,000	\$15,000
TOTAL	\$165,000	\$165,000	\$165,000

REFERENCES

1. The_World_Bank. *Fertility rate (total births per woman), Table*. 2013 [2 September 2013]; Word Development Indicators]. Available from: <http://data.worldbank.org/indicator/SP.DYN.TFRT.IN>.
2. Ministry_of_Health, U. and UNAIDS, *HIV and AIDS Uganda Country Progress Report 2014*. 2015.

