Upon completing the informed consent process, interested participants will be asked to sign or fingerprint a copy of the written informed consent to confirm that they understand the study and what is expected of them as a research participant. A copy of the signed consent form will be given to the participant for their records. After signing of the consent, participants will be considered enrolled as part of the sample goal of 150 uninfected women.

Enrolled women will participate in the outlined mixed-method study to evaluate prevalence and determinants of uptake and adherence (tenofovir plasma concentration >40ng/mL, taking >80% of dispensed pills) to daily, oral TDF/FTC PrEP during periconception among HIV uninfected Ugandan women reporting HIV-infected or unknown serostatus partners. To accomplish this, women will participate in quarterly study visits, HIV and pregnancy testing, questionnaires and safer conception/adherence group counseling sessions. Participants will be eligible to initiate PrEP at any time during the first 6 months of the 9-month (maximum) study follow-up period. Participants will receive a PrEP referral form to bring to the clinic if they chose to initiate PrEP outside of a scheduled study follow up visit.

Women who become pregnant or test positive for HIV during the 9-month follow-up period will complete exit activities (questionnaire and in-depth interview) and be referred to appropriate antenatal and/or HIV follow-up care.

Counseling

Comprehensive safer conception counselling: Enrolled women will be offered a package of safer conception counselling for uninfected women who want to conceive a child with an infected partner:

- Encourage partner testing and serostatus disclosure within the partnership.
- Encourage partner to initiate ART if he is eligible by national guidelines (CD4 cell count \leq 500 or in serodiscordant partnership),
- Delay sex without condoms until he achieves HIV viral load suppression or is on ART x 6 months,
- Consider contraception to delay pregnancy until safer conception strategies implemented
- Limit sex without condoms to peak fertility, and / or
- Consider sperm washing, donor sperm, and adoption as alternatives.

Safer conception counselling will occur at baseline and then quarterly thereafter in non-pregnant women

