Table 3. Data collection procedures					
Months	0	i*	3	6	9/stud exit
Laboratory					
Urine pregnancy test	x		x	x	x
HIV test	x		x	x	x
STI screen	x		x	x	x
STI Objective Testing	x			x	
STI Case Report Form	x			x	
Additional labs for women who initiate PrEP					
Creatinine		x	x	x	x
HBV serology		x			
Drug level adherence testing			x	x	x
Behavioral					
Safer conception counseling	x		x	x	x
Full questionnaire (See Table 2)	x				x
diary sexual behavior	x		x	x	x
Wisepill adherence data	x		x	x	x
In-depth interviews (See Aim 3)				x	x
Additional for women who initiate PrEP					
Adherence support	x	x	x	x	x
*i = PrEP initiation visit					
** Objective STI Testing will include: gonorrhoeae, chlamydia, trichomonas vaginalis, herpes and syphilis at baseline and month 6 for all participants and as needed based on screening at all other visits/exit					

finger with a small, single-use lancet, squeezing a small amount of blood (approximately 1-2 drops) into a sample collection pipette, transferring a drop of blood into a marked sample well and waiting approximately 10-20 minutes for results. Women who test positive will receive a second, confirmatory finger-pick test. Upon completion of confirmatory testing, women who were confirmed positive will receive post-test counselling and be referred for appropriate HIV care before being exited from the study.

Syndromic STI screening: All women will be offered syndromic STI screening at each study visit. Syndromic STI screening will be conducted by asking participants if they have experienced any STI symptoms (e.g. discharge, ulcers, itching). For women who endorse STI symptoms a confirmatory test will be performed, and they will receive treatment medications dispensed by a licensed medical professional team member (see STI treatment below),

Objective STI testing: Women who consent to participate in objective STI testing will complete objective STI screening tests at baseline, at the 6-month study visit or study exit (if exit occurs prior to the 6-month timepoint) independent of the syndromic STI screen (see above).

Women who endorse symptoms of STI, as determined by syndromic STI screening, during interim visits or at the 3-month study visit will have additional objective STI testing.

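### Aim 4.2 does not time PrEP exposure against the STI tests, so infections and sex acts that precede PrEP can be credited to PrEP

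*Combined protocol and SAP*

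**What the plan says.** Section XIV, Analysis, Aim 4, sets the contrast as women who choose PrEP against women who do not take it, and hypothesises that more condomless sex leads to more STIs in the first group. The power statement is "We would have 82% power for a difference of 43% (PrEP group) vs 20% (no PrEP group) using a Chi-square test", two-sided at 0.05. It rests on up to 150 women, an anticipated overall STI incidence of about 35%, and the expectation that "2 out of 3 women[75] will want to start PrEP". For the analysis, "we will use a logistic regression model predicting incident STIs over six months including PrEP in all models". The number of condomless sex acts is then added. If it is a significant predictor and the PrEP odds ratio drops substantially, the plan concludes that sex acts mediate the PrEP effect.

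Section V, Overview: "Participants will be eligible to initiate PrEP at any time during the first 6 months of the 9-month (maximum) study follow-up period".

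Section V, Objective STI testing: consenting women "will complete objective STI screening tests at baseline, at the 6-month study visit or study exit", the exit test applying when exit comes before month 6. Women with symptoms at interim visits or at month 3 are tested additionally.

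The only definition of initiation is in the Aim 1 analysis: collecting at least one three-month supply. Aim 4 neither repeats it nor replaces it with anything dated.

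**The concern.** The outcome window opens at enrolment and closes at the outcome STI test. PrEP exposure can begin anywhere inside that window, on its last day, or after a positive symptomatic test at month 3. Nothing in Aim 4.2 links the two clocks.

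Three errors follow if PrEP enters the model as ever/never. A woman who starts on the day of her outcome test is counted as exposed with no prior PrEP time. A woman who starts mid-window has infections from before the start counted against PrEP. And the mediator count includes sex acts that happened before PrEP, although a mediator must follow the exposure.

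At stake is the conclusion about PrEP and STI risk, which section IX presents as a crucial first step in designing PrEP programmes. A null result might partly reflect women not yet on PrEP. A positive one might partly reflect who starts late and who stays long enough to start.

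**Working it through.** **1. The two clocks side by side (outcome test at month 6)**

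| PrEP start | Months on PrEP before the outcome test | Share of window | Ever/never value |
|---|---|---|---|
| Enrolment | 6 | 1.0 | PrEP |
| Month 3 | 3 | 0.5 | PrEP |
| Month-6 visit | 0 | 0 | PrEP |
| Never | 0 | 0 | No PrEP |

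Rows 3 and 4 have the same exposure before the outcome but opposite labels.

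**2. The plan's own power figure**

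Inputs from Analysis, Aim 4: 150 women; two in three on PrEP, so n1 = 100 and n2 = 50; p1 = 0.43, p2 = 0.20; two-sided alpha 0.05.

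- Pooled risk = (100 × 0.43 + 50 × 0.20)/150 = 0.3533, which matches the anticipated 35%.
- SE under the null = √[0.3533 × 0.6467 × (1/100 + 1/50)] = 0.0828.
- SE under the alternative = √[0.43 × 0.57/100 + 0.20 × 0.80/50] = 0.0752.
- Power = Φ[(0.23 − 1.96 × 0.0828)/0.0752] = Φ(0.90) = 81.6%.

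Exact enumeration of the uncorrected chi-square test gives 82.1%. The printed 82% reproduces.

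**3. Sensitivity to what 43% means**

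*Reading A: 43% is the average risk among all choosers, late starters included.* Nothing changes: 81.6%.

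*Reading B: 43% is the risk with six full months on PrEP.* This is an assumption. Take constant monthly hazards, 20% as the six-month risk off PrEP, and late starters kept in the PrEP group.

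- h1 = −ln(0.57)/6 = 0.0937; h0 = −ln(0.80)/6 = 0.0372.
- Six-month risk for a start at month s = 1 − exp{−[h0·s + h1·(6 − s)]}.
- Start at month 3: 1 − exp(−0.3926) = 32.5%. Start at month 6: 20%.
- Uniform starts over months 0 to 6: mean 32.1%.
- Half at month 3, half at month 6: (32.5 + 20)/2 = 26.2%.

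With a share f of starters late, PrEP-group risk = (1 − f) × 43% + f × late-starter risk. Power then follows from the formula in step 2:

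| Late share f | Uniform: risk | Uniform: power | Months 3 and 6: risk | Months 3 and 6: power |
|---|---|---|---|---|
| 0% | 43.0% | 81.6% | 43.0% | 81.6% |
| 5% | 42.5% | 79.8% | 42.2% | 78.8% |
| 10% | 41.9% | 77.9% | 41.3% | 75.7% |
| 20% | 40.8% | 73.7% | 39.6% | 68.8% |
| 40% | 38.7% | 64.5% | 36.3% | 53.3% |

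The documents give no late-start share, so no row can be called the expected one.

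**4. Direction of bias**

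Under reading B, late starters pull the odds ratio toward 1. Two features of the design can push the other way. PrEP is self-selected, so late starters may already carry more than the 20% risk. And women exit on pregnancy or HIV infection (section V, Overview), so those who leave early have less time to become late starters. An ever-PrEP group may therefore have longer follow-up and more opportunity for an STI to be found. The net direction is not determined by the documents.

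**The case against.** The strongest reply is that the plan compares women who choose PrEP with women who do not, and sizes the groups by how many will want to start. On that wording 43% is naturally the average over all choosers. The inputs agree: 2/3 × 43% + 1/3 × 20% = 35.3%, the anticipated overall figure, with every starter counted at 43%. Reading B quietly lowers that overall incidence: at 20% late it becomes 33.9% (uniform) or 33.1% (months 3 and 6). This objection stands as far as power is concerned. A reader might infer that the 82% assumes six full months on PrEP for everyone and so is not delivered. The documents neither state that assumption nor give the late-start share needed to show a shortfall. Nor do they support a flat claim that the odds ratio is pulled toward 1.

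It can also be said that ever/never is itself inferred, since Aim 4.2 says only that PrEP is in the model, and that PrEP education at enrolment and immediate eligibility may keep late starts few. Both are fair. But the only initiation definition in the plan is an ever-type one, and late starts are provided for: Table 3 has a separate initiation visit, and section V provides a referral form for starting between scheduled visits.

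The objection does not reach the mediation claim. That claim concerns an effect of PrEP, and acts or infections before the first dose cannot be part of it, whatever 43% means.

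**Conclusion.** The concern holds as a problem of exposure definition. Aim 4.2 allows women with no PrEP time before their outcome test to count as exposed, and allows earlier infections and sex acts to be attributed to PrEP. The resulting bias in the odds ratio and in the mediation conclusion can go either way; its size depends on how many women start late and who they are, which the documents do not say.

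The power figure is correct for its stated inputs. It stands unchanged if 43% describes all choosers. Only under the assumption that 43% means six full months on PrEP, with constant hazards and a yes/no term, does it fall: about 78% to 76% with 10% late starters, 74% to 69% with 20%, and 65% to 53% with 40% (uniform starts versus starts split between months 3 and 6).

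**What to change.** In Analysis, Aim 4.2:

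- Define PrEP exposure relative to the STI tests, using the initiation date. Women who start on or after the day of the outcome test, or of the first positive test if earlier, are unexposed. Other starters contribute only time after the start.
- One workable form is the fraction of the baseline-to-outcome interval on PrEP, with interval length also accounted for. Without that, an enrolment starter who exits at month 3 scores the same 1.0 as one followed for six months. A time-varying or landmark definition would also serve.
- In PrEP users, count only condomless sex acts after the start as possible mediators, relative to the length of time covered.
- Keep ever/never PrEP as a descriptive comparison.
- Keep the 82%, adding that it holds if 43% is the average risk among all women who choose PrEP. If full exposure was meant, show power over a range of late-start shares rather than one replacement figure.

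The cost is SAP wording and derived variables. The initiation date must already be known, because Aim 2 measures drug level three months after initiation, and the sex diaries are kept monthly. No new data or participants are needed. The downside of the fraction form is an odds ratio expressed per full window on PrEP, which assumes an effect in proportion to time on PrEP.

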Testing of phlebotomy samples for Syphilis Treponemal Ab and non-treponemal as well as the preprocessing and serum extraction for HSV2 Ab testing will be performed at the MUST Research lab. (see below)

Serological testing for HSV2 (by ELISA) will be performed at Makerere University microbiology lab under [name]. [name] lab has expertise in performing ELISA serology testing for HSV2 and has published on the sensitivity and specificity of this assay methodology among HIV-infected and uninfected Ugandans [66].

Turnaround time for all testing (with the exception of HSV2 Ab) will be approximately two hours, allowing women with positive STI test results to be seen for follow-up clinical evaluation and treatment as well as counselling around partner referral and treatment at the same study visit. Women with an active outbreak of suspected HSV2 based on clinical exam will be offered acyclovir prior to objective confirmatory results as per standard of care.

All biological tests including pregnancy testing, HIV testing, and STI syndromic screenings will be performed by clinical study staff in a private room located at the ISS clinic.

STI Vaginal Swab Testing (MUST Microbiology Lab):

The MUST Microbiology lab has been fully functional for over ten years. The lab has expertise in various lab modalities including GeneXpert and run over 800 samples via GeneXpert each month which include TB sputum, TB CSF, TB stool, HIV RNA, and HPV testing ([67]). The MUST Microbiology lab's GeneXpert procedures have been externally validated by the Ugandan Ministry of Health as well as internally validated via Cepheid QA/QC procedures ([67]). GeneXpert testing will be utilized to test for CT, NG and TV.

Number of samples: Objective STI testing will be offered to up to 150 women (this number will vary in light of our study currently in enrolment).

All women will either self-collect or undergo nurse-collected vaginal swabs (2 swabs each) at study initiation, and either at 6 months or at the time of study exit prior to 6 months. Women with STI symptoms at the 3 month study visit will also undergo additional vaginal swab testing, and given our knowledge of symptomatic STIs, we anticipate this to be no larger than 15% of our study population.[68] Therefore we anticipate collecting no more than 645 vaginal swabs in total. The second vaginal swab collected at each instance will be used for quality assurance or stored for future testing.

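### Aim 4.2 compares incident STIs between women who do and do not choose PrEP without naming baseline STI status as a covariate, so earlier risk may be mistaken for a PrEP difference, or may hide one

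*Combined protocol and SAP*

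**What the plan says.** Section XIV, Analysis, Aim 4, hypothesises more incident STIs in women who choose PrEP (Hypothesis 4.2). The stated analysis reads "we will use a logistic regression model predicting incident STIs over six months including PrEP in all models", and condomless sex acts are added in a second step. No other covariate is named. The sizing sentence reads "We would have 82% power for a difference of 43% (PrEP group) vs 20% (no PrEP group) using a Chi-square test", and its inputs are "we anticipate the incidence of any STI will be approximately 35%[74] and that 2 out of 3 women[75] will want to start PrEP".

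In the same section, baseline STI is the outcome of the Aim 4.1 model. That model is carried to the six-month data only to see how well it predicts, not to adjust the PrEP comparison. The P<0.20 confounder screen is written under Aims 1 and 2 and is not repeated under Aim 4.

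Other sections set the timing:

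- Section II (Specific Aims, Aim 4): the comparison is by the woman's own choice of PrEP.
- Section V (Overview): PrEP may be started at any time in the first six months.
- Section V (Objective STI testing) and Table 3: women who consent are tested at baseline and at month 6, or at exit if earlier.
- Section VI (STI Testing, General): results other than HSV-2 antibody take about two hours, "allowing women with positive STI test results to be seen for follow-up clinical evaluation and treatment" at the same visit.
- Section V (STI Treatment): women who test positive are treated and receive medication for their partners.

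**The concern.** In a non-randomised comparison, a baseline measurement of the outcome is the natural first covariate. Here a woman can learn that she has an STI before she decides about PrEP. The study's own framework (Section II, Table 2) lists risk perception among the factors that may influence PrEP initiation, and a new diagnosis could change it. The same result may mark women more likely to be infected again. If both links exist, the groups differ in prior STI risk before PrEP can act, and a model with PrEP alone attributes that difference to PrEP.

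Section IX says that understanding STI risk in these women is a step towards designing PrEP programmes, so a selection artefact would carry weight. The mediation conclusion in Aim 4.2 is also exposed, because it rests on how far the same PrEP odds ratio falls when condomless acts are added.

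**Working it through.** **1. The plan's own figure.** Inputs from Section XIV, Aim 4: N = 150, two thirds on PrEP (100 and 50), 43% and 20%, two-sided alpha 0.05.

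- Pooled incidence = (100×0.43 + 50×0.20)/150 = 53/150 = 35.3%, which matches the stated 35%.
- Null SE = √(0.353×0.647×(1/100 + 1/50)) = 0.0828.
- Alternative SE = √(0.43×0.57/100 + 0.20×0.80/50) = 0.0752.
- Power = Φ((0.23 − 1.96×0.0828)/0.0752) = Φ(0.901) = 81.6%. Exact enumeration of the uncorrected chi-square gives 82.1%.

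The stated 82% is reproduced. It belongs to a crude comparison with a design odds ratio of (0.43/0.57)/(0.20/0.80) = 3.02.

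**2. What omitting baseline STI could do when PrEP has no effect.** Taken from the plan: N = 150, 2/3 uptake, 35% incidence. Assumed, because the documents give no figures: baseline prevalence π of 20% to 50%, and the odds ratios linking baseline STI to PrEP start and to incident STI.

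Let u₁ and u₀ be uptake, and i₁ and i₀ incidence, in women with and without baseline STI. Each pair is solved so that the overall figures stay at 2/3 and 35%. Then:

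- Baseline STI among PrEP users: b₁ = π·u₁/(2/3). Among non-users: b₀ = π·(1−u₁)/(1/3).
- Expected incidence in each group: q = b·i₁ + (1−b)·i₀.

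Central case (π = 35%, odds ratios 2 and 3): u₁ = 76.2%, u₀ = 61.5%, i₁ = 51.5%, i₀ = 26.1%.

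- b₁ = 0.35×0.762/0.667 = 0.400 and b₀ = 0.35×0.238/0.333 = 0.250.
- q₁ = 0.400×0.515 + 0.600×0.261 = 36.3%, and q₀ = 0.250×0.515 + 0.750×0.261 = 32.5%.
- Spurious odds ratio = 1.18.

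The rejection rate uses the same normal approximation as step 1, two-sided.

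| Baseline STI | OR with PrEP start | OR with incident STI | PrEP | No PrEP | Spurious OR | Rejection |
|---|---|---|---|---|---|---|
| 20% | 1.5 | 2 | 35.3% | 34.3% | 1.05 | 5.1% |
| 35% | 2 | 3 | 36.3% | 32.5% | 1.18 | 7.2% |
| 35% | 3 | 3 | 36.9% | 31.2% | 1.29 | 10.4% |
| 50% | 3 | 5 | 38.0% | 28.9% | 1.51 | 19.0% |
| any | 1 | any | 35.0% | 35.0% | 1.00 | 5.0% |
| 20% | 0.5 | 2 | 34.4% | 36.3% | 0.92 | 5.7% |
| 35% | 0.5 | 5 | 33.0% | 38.9% | 0.77 | 11.3% |

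A logistic model with PrEP as its only term estimates this same crude odds ratio.

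**3. How much adjustment recovers.** If baseline STI is the only confounder, adjusting for it brings rejection back to about 5%, but only because the assumption guarantees it. Suppose instead that baseline STI is a proxy for an unmeasured risk level. Assume 35% of women are high risk and, for high-risk versus other women, baseline STI 60% versus 21.5%, uptake 85% versus 57% and incidence 55% versus 24%. Simulated cohorts of 150 with no PrEP effect then reject in about 18% unadjusted and about 15% adjusted (17% to 19% and 13% to 15% across repeated runs).

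**4. Room in the model.** With about 53 events, PrEP, condomless acts and baseline STI leave 53/3 ≈ 18 events per parameter. Adding HSV-2 serostatus leaves 53/4 ≈ 13.

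**The case against.** Several points on the other side stand.

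- A reader might infer that a crude chi-square is the mandated test of Hypothesis 4.2. It is not. The chi-square appears only in the power sentence, and the stated analysis is logistic regression. The reference to all models also leaves room for further covariates. The criticism is that none beyond condomless acts is specified.
- A reader might infer that every woman in the incidence analysis has a baseline result. The documents do not guarantee this. Objective testing was added by amendment during enrolment, needs consent, and covers up to 150 women depending on start date (Sections III, V and VI).
- Both links are assumed. The documents do not say whether the two-hour result comes before the PrEP decision. Treating the woman and supplying partner medication may weaken the link to later infection.
- Larger distortions can be produced. Uptake of 90% versus 54% and incidence of 60% versus 21.5% by baseline STI give 14.2 points and about 40% false positives. That needs odds ratios of about 7.7 and 5.5, which nothing in the documents supports.
- The Aim 1 analysis already compares baseline characteristics of women who do and do not start PrEP, which might expose an imbalance. It would not correct the Aim 4.2 estimate.

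None of this justifies leaving a measured baseline form of the outcome out of a self-selected comparison.

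**Conclusion.** The concern holds as a gap in the specified model. Run as written, Aim 4.2 omits baseline STI status from the PrEP comparison. The size and direction of the resulting bias are unknown. Under the assumed range with a positive link to uptake, the spurious odds ratio is about 1.05 to 1.5 and the false-positive rate about 5% to 19%. With no link to uptake there is no bias. With a negative link (odds ratio 0.5) the spurious odds ratio is about 0.77 to 0.92, which works against Hypothesis 4.2.

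Two stronger readings are not supported. Within this range baseline STI alone does not produce the planned contrast: the largest spurious gap is 9.1 points, against 23. Nor would adjustment make the comparison unconfounded, as step 3 shows. The 82% power figure is correct for the crude comparison it describes.

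**What to change.** Amend Section XIV, Analysis, Aim 4, as follows:

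- Include baseline STI (any curable STI, yes or no) as a fixed covariate in every Aim 4.2 model, both with and without condomless acts.
- Base the conclusion on Hypothesis 4.2 on the adjusted PrEP odds ratio, with its confidence interval, and show the unadjusted comparison alongside.
- Count incident HSV-2 only in women seronegative at baseline. For the other STIs, use baseline HSV-2 serostatus as a covariate.
- State how many women lack a baseline result and how they are handled.
- State that confounding by unmeasured risk remains.

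No new visit or assay is needed for women tested at enrolment. The cost is one or two extra parameters against about 53 expected events if all 150 women are tested, and fewer events if they are not. Women without a baseline result cannot enter the adjusted model. The 82% should be labelled as the power of the unadjusted comparison.

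### Aim 4.2's mediation rule tests only whether condomless acts predict STI, so it can name a mediator of the PrEP effect by chance when PrEP is related to neither acts nor STIs

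*Combined protocol and SAP*

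**What the plan says.** Section XIV, Analysis, Aim 4, sets out Hypothesis 4.2 as a chain: "We expect a higher incidence of condomless sex leading to a higher STI incidence among women who choose PrEP" than among those who do not. The analysis is a logistic model for incident STI over six months with PrEP in every model; the number of condomless acts is then added. The decision rule has two parts, namely that the number of "condomless sex acts is a significant predictor and there is a substantial reduction in the odds ratio (OR) for PrEP" once acts are included. If both are met, "then we will conclude that this is a mediator of the PrEP effect".

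The same section gives the planning figures: up to 150 women, the expectation "that 2 out of 3 women[75] will want to start PrEP", overall STI incidence of about 35%, and 82% power for 43% versus 20% by a two-sided chi-square test at 0.05. That power statement concerns the total PrEP-STI difference. No error rate or power is given for the mediation rule.

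Section V, Sexual Behavior, plans to explore differences in diary data between women who do and do not start PrEP. It names no test and is not linked to the rule.

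**The concern.** The hypothesis needs two links: PrEP users have more condomless sex, and more condomless sex brings more STIs. The rule tests only the second. That link is plausible whatever PrEP does, so its significance says little about PrEP. The other input is a bare change in a point estimate, without a standard error, interval or cut-off.

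Any chance difference in acts between the two groups moves the PrEP OR when acts are added. If PrEP users happen to report more acts, the OR falls and the rule can fire. A fall also counts when the unadjusted OR is below 1, where it moves away from 1 and explains no harmful effect. This is separate from self-selection into PrEP; it would occur under random assignment too.

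At stake is the plan's only stated route to concluding that PrEP raises STIs through more condomless sex. Section IX describes understanding STI risk in this group as a first step towards designing PrEP programmes, so a spurious conclusion of that kind would matter.

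**Working it through.** **Inputs from Section XIV, Aim 4.** 150 women split 2:1, so 100 PrEP and 50 no PrEP; overall STI incidence 35%; two-sided alpha 0.05.

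**The plan's own figure.** Pooled incidence = (43 + 10)/150 = 35.3%, which agrees with the stated 35%. Null SE = sqrt(0.353 × 0.647 × (1/100 + 1/50)) = 0.0828. Alternative SE = sqrt(0.43 × 0.57/100 + 0.20 × 0.80/50) = 0.0752. Then z = (0.23 − 1.96 × 0.0828)/0.0752 = 0.90, giving power 81.6%. Exact enumeration gives 82.1%. The stated 82% is reproduced.

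**Assumptions not in the documents.** Strength of the acts-STI association (OR 1.0 to 2.5 per SD of acts); distribution of acts (normal or negative binomial); meaning of a substantial reduction (a relative fall of 10% or 20% in the OR).

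**Analytic check.** With PrEP unrelated to acts, the difference in mean acts has SE sqrt(1/100 + 1/50) = 0.173 SD. At an acts OR of 2.0 per SD, the change in the PrEP log-OR has SD of about ln 2 × 0.173 = 0.12. A 10% fall is a log change of ln 0.9 = −0.105, so the probability is about Φ(−0.105/0.12) = 19%. At that strength acts are significant in about 97% of trials, so the significance condition filters out little.

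**Simulation.** 6,000 trials per cell, PrEP unrelated to acts and to STI, both logistic models fitted. The rule fires if the Wald p for acts is below 0.05 and the OR falls by at least the threshold. Ranges are normal versus negative-binomial acts.

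| Acts OR per SD | Rule, 10% fall | Rule, 20% fall | 10% fall, crude OR > 1 | 10% fall, crude OR > 1 and significant |
|---|---|---|---|---|
| 1.0 | 0.3-0.4% | 0.02-0.03% | 0.05-0.1% | 0% |
| 1.25 | 2.5-2.7% | 0.1-0.2% | 0.9-1.1% | below 0.1% |
| 1.5 | 8.0-8.2% | 0.9-1.0% | about 3.5% | 0.2-0.3% |
| 2.0 | 17.7-18.3% | 3.9-4.1% | about 8.5% | 0.3-0.4% |
| 2.5 | 24.4-26.0% | 8.1-8.7% | 11.8-12.2% | 0.5-0.6% |

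Repeat runs agree to within a point or two. At a 10% fall and acts OR 1.5 to 2.5, the total PrEP effect has p > 0.05 in 93-96% of the false declarations, and the crude PrEP OR is below 1 in about half.

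**With the planned PrEP effect.** Under 43% versus 20% with no mediation, the rule fires at a 10% fall in about 2-5% of trials. With a true PrEP OR above 1, adding a predictor of STI to a logistic model tends to raise the PrEP OR, so a fall is less common.

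**With a PrEP-acts test added.** Also requiring significantly more acts among PrEP users cuts the false rate to at most 2.9% in every null scenario.

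**The case against.** The strongest reply is that a mediator of the PrEP effect presupposes a PrEP effect. The hypothesis is directional, a powered test of the PrEP-STI difference comes just before the rule, and a sensible analyst would look for mediation only after finding a difference. Under that reading the false rate is 1% or less. This stands as a limit on size, but the text does not make the test a condition and the rule says that mediation will be concluded. Requiring only a crude OR above 1 still leaves about 8.5% and 12% at acts ORs of 2.0 and 2.5 with a 10% fall.

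Second, the size rests on figures that the documents do not give. That also stands. If acts predict STI weakly, the rule is conservative, and error in self-completed diaries could weaken the association. At a 20% fall, of the strengths examined, only an OR of 2.5 takes the literal rule above 5%. Yet the missing threshold is the plan's own gap: at acts OR 2.0 the rate runs from about 4% to 18% depending on a cut-off that could be chosen after the data are seen.

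Third, the exploratory comparison of sexual behaviour in Section V would show whether acts differ by PrEP use. It would help a reader, but the conclusion does not depend on it.

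A reader might infer that about a fifth of mediation claims from this study would be false, or that the rule fails whatever PrEP does. Neither is supported. The percentages are rates per trial under a null, at chosen association strengths, and the rate is about 2-5% under the plan's own effect.

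**Conclusion.** The point holds in limited form. Followed literally, the rule can declare mediation from chance imbalance in acts, because the fall in the PrEP OR is untested and undefined and no PrEP-acts or PrEP-STI association is required. At a 10% fall the false rate exceeds 5% once acts predict STI with an OR of about 1.5 per SD or more, reaching about 18% at 2.0 and 23-26% at 2.5; at a 20% fall it exceeds 5% only near 2.5. These figures assume 100 versus 50 women, 35% incidence and PrEP unrelated to both acts and STIs.

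The problem arises mainly when PrEP has little or no effect on STIs. The documents do not support reading it as a flaw in the study's main results: the uptake and adherence aims do not use this rule, and Aim 4.2 is a secondary, observational question. The change is worth making, but the point is not critical.

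**What to change.** Replace the rule in Section XIV, Analysis, Aim 4:

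- Estimate the PrEP-acts association, and the acts-STI association adjusted for PrEP.
- Report the indirect effect with a bootstrap 95% CI, on a scale named in advance.
- State evidence for the acts pathway only if that CI excludes zero in the harmful direction and both path estimates are positive (more acts with PrEP, more STIs with more acts). The sign condition is needed because two negative paths also give a positive indirect effect.
- Otherwise report the total PrEP-STI association and the change in OR descriptively, with no mediation conclusion.

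The cost is SAP wording and a short bootstrap; diaries are already planned for all women regardless of PrEP. The downside is somewhat fewer mediation declarations. With a true 0.5-SD difference in acts and an acts OR of 2.0 per SD, requiring both paths to be significant gave about 77-79% power, against about 81-93% for the present, uncalibrated rule at a 10% fall. Those power figures are for joint significance, used as a stand-in for the bootstrap interval. A small check of the interval itself (500 trials per cell) gave a false rate of about 1-3%.
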